**Table 5–2 : Classification of ADA status**

1.	Pre ADA negative and treatment-emergent ADA negative	Study participant who were negative at Baseline and negative at all sampling points post treatment at all timepoints
2.	Pre ADA negative and treatment-(emergent) induced ADA positive	Study participant who were negative at Baseline and positive at any sampling point post treatment. This group also included study participants who had a missing pre-treatment sample (either missing or insufficient volume) with 1 or more positive post-treatment samples.
3.	Pre ADA positive and treatment-emergent reduced ADA	Study participants who were positive at Baseline, and negative at all sampling points post treatment all timepoints.
4.	Pre ADA positive and treatment-emergent unaffected ADA positive	Study participants who were positive at Baseline and were positive at any sampling point post treatment with titer values of the same magnitude as Baseline (i.e., less than a predefined fold difference from the Baseline value of 4.11).
5.	Pre ADA positive and treatment-emergent ADA boosted positive	Study participant who were positive at Baseline and were positive at any sampling point post treatment with increased titer values compared to Baseline (greater than a predefined fold difference increase of 4.11 from Baseline value which is defined within the validation of the assay).
6.	ADA inconclusive	Study participants who were positive at Baseline and some post-treatment samples were missing, while other post-treatment samples were negative.
7.	Treatment emergent ADA positive	Combination of 2 and 5
8.	Pre-treatment ADA positive	Combination of 3, 4 and 5
9.	Missing	Study participants who were negative at Baseline or missing their Baseline assessment, were not positive at any post-Baseline visit, and have at least one missing post-treatment scheduled assessment.

Analysis:

Immunogenicity will be assessed through summary tables and figures and listing of individual results by study participant. All analyses will be run on the SS, unless specified otherwise. For all

tabulations, percentages will be calculated based on the number of study participants with non-missing data.

- Individual participant concentration-time profiles of CZP will be displayed graphically in linear and semi-logarithmic scale and grouped by MTX use at screening.
- All individual study participant-level ADA results will be listed for all study participants. This will include the screening assay, confirmatory assay, and titer (if applicable).
- Summary table displaying the number and percentage of study participants with a positive ADA, negative ADA, inconclusive or missing ADA sample status at the time of each visit by treatment group. [Note that in case of presence of pre-ADA, no differentiation can be made between pre-ADA and treatment emergent ADA (either newly induced or boosted ADA). Note this table is not be used for incidence interpretation].
- Based on the overall ADA study participant classification above from Table 5-2, the following will be determined and presented: summary tables displaying the number and percentage of study participants in each of ADA participant status categories (1–9), with the denominator being the total number of study participants having an individual ADA participant category defined during the corresponding analysis period and treatment group. (All study participants will be assigned to a category in this table and should not be confused with ADA incidence that is defined below).

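### SAP Table 5-2 is not guaranteed to place each participant in exactly one ADA category, and its Pre-treatment ADA positive row leaves out some baseline-positive participants

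*SAP*

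**What the plan says.** SAP Section 5.5.1.1.2 gives each sample one of four statuses: positive, negative, inconclusive (a negative result with drug above the assay's tolerance limit) or missing. Table 5-2 then classifies participants. For those positive at Baseline:

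- Category 3 (reduced): "Study participants who were positive at Baseline, and negative at all sampling points post treatment all timepoints".
- Category 4 (unaffected): "positive at any sampling point post treatment with titer values of the same magnitude as Baseline", explained as "less than a predefined fold difference from the Baseline value of 4.11".
- Category 5 (boosted): "positive at any sampling point post treatment with increased titer values compared to Baseline", explained as "greater than a predefined fold difference increase of 4.11 from Baseline value".
- Category 6 (inconclusive): "Study participants who were positive at Baseline and some post-treatment samples were missing, while other post-treatment samples were negative".
- Category 8 (pre-treatment positive): "Combination of 3, 4 and 5".

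Category 9 (missing) is open only to participants negative or missing at Baseline, never positive afterwards, with at least one post-dose sample missing. Category 7 is the union of 2 and 5.

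The analysis list that follows reports counts and percentages for categories 1–9, using as denominator the participants who have a category. It adds: "All study participants will be assigned to a category in this table". Under the incidence and prevalence heading, pre-antibody prevalence counts every participant with a positive Baseline sample, and the incidence denominator removes only those classed as inconclusive.

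**The concern.** A table that assigns everyone needs elementary rows that do not overlap and leave nobody out. Rows 4 and 5 each need only one qualifying sample, and nothing says which wins. Row 6 covers only a mix of missing and negative samples in baseline-positive participants. It does not mention the inconclusive sample status that the same section creates.

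Four outputs are exposed. The category table can count a person twice or not at all. Category 8 can disagree with the prevalence numerator, although both describe participants positive before treatment. The incidence denominator drops only category 6 as narrowly defined. A baseline-positive participant with no post-dose sample therefore stays in it, although unable to show boosting, unless the SAP's general rule on non-missing data is applied to remove them. Lastly, the concentration plot is coloured by categories 1, 3, 4 and 7. Because 7 contains 5, a participant in both 4 and 5 has two colours.

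**Working it through.** The plan gives no figure to reproduce, so the check lists every possible result pattern and applies Table 5-2 literally. Rows 1–6 and 9 are tested; rows 7 and 8 are unions by design.

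**Inputs.** There are four post-Baseline ADA samples: Weeks 6, 12, 24 and SFU (Protocol Section 1.3; SAP Section 5.1.1.1.4). The sample statuses and the 4.11 limit come from SAP Section 5.5.1.1.2. For a baseline-positive participant, each sample is negative (N), inconclusive (I), missing (M), positive within 4.11-fold (S), positive more than 4.11-fold higher (B) or positive more than 4.11-fold lower (R). That gives 6^4 = 1296 patterns. For Baseline negative or missing, titer size is irrelevant, so there are 4^4 = 256 patterns each.

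Table 5-2 does not say whether category 4's fold difference runs in both directions, so both readings were counted.

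**Baseline positive, fold difference read in both directions**

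- In both 4 and 5 (at least one S and one B): 1296 − 2×5^4 + 4^4 = 1296 − 1250 + 256 = 302.
- In none: 4^4 = 256 patterns have no S and no B. Remove 1 (all N, category 3) and 2^4 − 2 = 14 (N and M mixed, category 6): 241.
- In exactly one: 1296 − 302 − 241 = 753.

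**Baseline positive, fold difference read as an increase only (R counts as category 4)**

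- In both: 1296 − 4^4 − 5^4 + 3^4 = 1296 − 256 − 625 + 81 = 496.
- In none: 3^4 − 1 − 14 = 66.
- In exactly one: 1296 − 496 − 66 = 734.

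The 66 consist of one all-missing pattern and 81 − 16 = 65 with at least one inconclusive sample and no positive one. The two-directional reading adds 256 − 81 = 175 patterns whose only positive titers are reduced: 66 + 175 = 241. Under either reading, 14 patterns fall in category 6 and so outside category 8.

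**Baseline negative.** Never positive, none missing, at least one inconclusive: 2^4 − 1 = 15 of 256 fit no row.

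**Baseline missing.** Never positive and none missing: 2^4 = 16 of 256 fit no row, including the pattern with all samples negative.

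**Cases**

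| Baseline | Post-dose samples | Category |
|---|---|---|
| Titer 64 | 64 (1x), 512 (8x), N, N | 4 and 5 |
| Positive | M, M, M, M | none |
| Positive | I, I, I, N | none |
| Positive | R, R, R, R | none, or 4 if only increases count |
| Positive | N, M, N, N | 6, so not in 8 |
| Negative | N, N, I, N | none |
| Missing | N, N, N, N | none |

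**Effect on the table.** Take six baseline-positive participants with patterns SBNN, IIIN, NMNN, NNNN, SSSS and BBBB. The rows give category 3 = 1, 4 = 2, 5 = 2 and 6 = 1, a total of 6. That is right only by accident, because one double count offsets one unplaced participant. The SAP's denominator is the 5 who have a category, so the elementary percentages total 6/5 = 120%. Adding rows 3, 4 and 5 gives 5, and counting people in those rows gives 4, but the prevalence numerator is 6.

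**The case against.** Intent is fairly clear on the overlap. By its label, a boosted participant is not an unaffected one. The first-occurrence summary also dates treatment-emergent positivity in pre-positive participants from the first sample above the fold limit. Category 5 is probably meant to override 4. That stands as intent, but no sentence states it, and it does nothing for the gaps or for category 8.

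The reduced-titer gap depends on the two-directional reading. That also stands, and it accounts for 175 of the 241 unplaced patterns. The other 66 remain.

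The amendment summary in SAP Section 8.2 prints a broader category 6 with a catch-all. It is not the current table and is not relied on here. It would cure neither the overlap nor category 8.

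Practical reach is unknown. Participants are CZP-naive, and the documents give no expected pre-antibody prevalence. They also give no drug-tolerance limit, which decides how often samples are inconclusive. Individual results and titers are listed in any case, positive samples are marked on the plot whatever its colours, and prevalence is taken from the Baseline sample, so it is correct whatever category 8 shows.

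A reader might infer more than the documents support:

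- That the table cannot add up. It may; it is only not guaranteed to, since an overlap and a gap can cancel and most of the problems need a baseline-positive participant.
- That percentages may total less than 100%. This does not follow, because an unplaced participant also leaves the denominator.
- That ADA status is the main explanation for low exposure in this study. No section says so.

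**Conclusion.** Table 5-2 is wrong as written, and the defect is limited. It permits double classification, leaves some participants without a row despite the statement that all are assigned, and defines category 8 so that it can fall short of the prevalence numerator. The overlap, the all-missing and inconclusive gaps, and the category 8 omission hold under either reading of fold difference. Only the reduced-titer gap depends on it.

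For baseline-positive patterns the size is 302 double and 241 unplaced of 1296, or 496 and 66 if only increases count. These weight every pattern equally and say nothing about how many participants will be affected. With 30 enrolled, one misplaced participant is 1/30 = 3.3 percentage points. The inconclusive gap needs no baseline-positive participant.

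The consequences stay within the ADA outputs, which both documents list under other objectives. The primary parameters, Cmin and AUC, are summarized by MTX use at screening (SAP Section 5.3.2), not by ADA category, and are unaffected.

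**What to change.** Replace the row definitions with a ranked rule.

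**Baseline positive**

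1. Any post-Baseline titer more than 4.11-fold above Baseline: category 5.
2. Otherwise any positive post-Baseline sample, including reduced titers: category 4.
3. Otherwise all scheduled samples negative: category 3.
4. Otherwise (any sample missing or inconclusive): category 6.

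**Baseline negative or missing**

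- Keep categories 1 and 2.
- Baseline negative, never positive, with inconclusive but no missing samples: category 6.
- Baseline negative, never positive, with any sample missing: category 9, as now.
- Baseline missing and never positive: category 9 in all cases.

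Define category 8 directly as every participant with a positive Baseline sample. It cannot be written as 3+4+5+6, because the revised category 6 also holds some baseline-negative participants. Restate the incidence denominator in terms of the revised category 6. Add a program check that categories 1–6 and 9 sum to the Safety Set.

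Under this rule all 1296 + 256 + 256 = 1808 patterns fall in exactly one elementary category. The six participants above become category 3 = 1, 4 = 1, 5 = 2 and 6 = 2, with category 8 equal to 6.

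The cost is SAP and TFL wording and a few program lines. No new data are needed.

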#### Incidence and prevalence:

- Total prevalence of pre-Ab overall and by treatment group. Total prevalence of pre-Ab:  $n/NN$  % number of participants that have a pre-ADA positive ADA sample status, with NN being the denominator defined as all participants having an evaluable baseline ADA sample.
- Overall ADA incidence and by treatment group. Treatment-Emergent Anti-CZP Antibody Positivity Activity for combined results of treatment-boosted ADA-positive participants and treatment induced ADA-positive participants.  $n/N$  % of participants that are treatment emergent, with N being the denominator defined as all participants except the participants categorized as inconclusive.
- Summary tables of the time point of the first occurrence of treatment emergent (TE) ADA positivity (i.e first ADA sampling time point with ADA positive status if participant is pre-ADA negative or first ADA sampling time point with fold difference increase from Baseline > the MSR if participant is pre-ADA positive) for study participants in category 2 and 5. The table will summarize the number and percentage of TE ADA positive participants who present first occurrence of TE ADA positivity at the specified time point and will include the cumulative number and cumulative percentage of participants at each time point. In case of ADA samples with missing or inconclusive status before the first ADA sampling time point considered TE ADA positive, the time point of the first occurrence of TE ADA positivity will be reported as  $\leq$  than the respective ADA time point. In case of pre-ADA present in more than 10% of the study participants, the table is split out between ADA participant category 2 and 5. The denominator for % calculations will be the total number of TE ADA positive participants.
- Number and percentage of study participant Baseline Anti-CZP status and Treatment-Emergent Anti-CZP Antibody Status will be summarized during the entire study. The change in category from Baseline ADA status including ADA-, ADA+, Missing and total will be presented in

shift tables at each post-Baseline treatment treatment-emergent anti-CZP antibody status. Treatment Treatment-Emergent Anti-CZP Antibody Status will be categorized as below:

- Negative : Treatment Treatment-Emergent Anti-CZP Antibody Status is ADAb-
  - Positive <512 : Treatment Treatment-Emergent Anti-CZP Antibody Status is ADAb+ and ADAb titer is less than 512.
  - Positive 512-<=1024: Treatment Treatment-Emergent Anti-CZP Antibody Status is ADAb+ and ADAb titer is greater than 512 and less than or equal to 1024.
  - Positive>1024: Treatment Treatment-Emergent Anti-CZP Antibody Status is ADAb+ and ADAb titer is greater than 1024.
  - Any positive : Study participants having treatment-emergent ADAb+.
  - Total : total Treatment Treatment-Emergent Anti-CZP Antibody Status
- Number and percentage of study participant Anti-CZP titer by visit will be summarized during the entire study. ADAb titer will be categorized as below:
    - Negative : The ADAb status is ADAb-
    - <=32 : The ADAb titer result is less than or equal to 32.
    - >32-128: The ADAb titer result is greater than 32 and less than or equal to 128.
    - >128-512: The ADAb titer result is greater than 128 and less than or equal to 512.
    - >512-1024: The ADAb titer result is greater than 512 and less than or equal to 1024.
    - >1024-4096: The ADAb titer result is greater than 1024 and less than or equal to 4096.
    - >4096: The ADAb titer result is greater than 4096.

A listing will be presented showing the CZP concentrations and ADAb measurements in the same output in adjacent columns, based on the SS. The listing will include the CZP concentration and ADAb status (positive or negative) and screening assay results (PS or NS) and confirmatory assay results if applicable (NI or PI), together with the titer if applicable. In addition, the time since the administration of study medication will be reported (in days). ADAb samples that are negative but have drug concentration above the drug tolerance characteristics of the assay will be flagged.

Time course plots of all individual CZP plasma concentrations profiles (each participant corresponding to a line) (spaghetti plot) with identification of the individual ADA participant category using different colors ( categories 1, 3,4 and 7. If not sufficient participants in category 3 and 4, these could be combined for this plot). These plots will be produced on a linear and semilogarithmic scale and multi-panel per treatment group. Individual samples with positive ADA sample status will be visualized using a symbol or a red dot. Dosing nominal time points should be indicated below the x-axis. A similar plot may be considered for PD endpoints. The plot may be stratified based on MTX use at baseline/screening.

Finally, individual participant plots will be presented displaying the ADAb titer and CZP concentrations overlaid on the same figure. The figure will also show the timing and dose of each administration of CZP received during the study. The ADAb data will be plotted using a semi-logarithmic scale. ADAb samples that are negative but have drug concentration above the drug tolerance characteristics of the assay will be flagged on the plot.

The rules for handling values that are BLQ in the CZP concentration data are described in [Section 5.5.1.1.1](#). For the ADAb data, any negative results for which there are no titers (as applicable) available at a specific visit will be substituted with 0.001 for the purpose of the figure.

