## 4 POPULATIONS FOR ANALYSIS

The following analysis sets will be used in the study:

- All Study Participants (ASP) will include those study participants who are confirmed as having signed the ICF form to participate in the study.
- The Safety Set (SS) will include all study participants enrolled who receive  $\geq 1$  injection of study medication. Safety variables will be summarized using the SS.
- The Pharmacokinetic Set (PKS) is a subset of the SS, consisting of study participants who have provided plasma samples with measurable concentrations (with recorded sampling time) on at least 1 visit, and who have no important protocol deviations affecting the PK parameters.

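### The ADA incidence denominator does not say what happens to participants classed as Missing, and it conflicts with the SAP's own non-missing-data rule

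*SAP*

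**What the plan says.** All of this is in SAP 5.5.1.1.2 unless another section is named.

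- **Incidence.** The numerator is the "combined results of treatment-boosted ADA-positive participants and treatment induced ADA-positive participants", which are categories 5 and 2 of Table 5–2. The denominator is described "with N being the denominator defined as all participants except the participants categorized as inconclusive".
- **Category 6, ADA inconclusive.** "Study participants who were positive at Baseline and some post-treatment samples were missing, while other post-treatment samples were negative".
- **Category 9, Missing.** Participants who were negative or unmeasured at baseline, "were not positive at any post-Baseline visit, and have at least one missing post-treatment scheduled assessment".
- **General percentage rule.** For all tabulations, "percentages will be calculated based on the number of study participants with non-missing data".
- **Analysis set.** "All analyses will be run on the SS, unless specified otherwise". Under SAP section 4 the Safety Set "will include all study participants enrolled who receive" at least one injection. No ADA sample is required for entry.
- **Prevalence.** The bullet just above incidence limits its denominator to participants with an evaluable baseline ADA sample. The incidence bullet has no matching restriction on post-baseline samples.
- **Sampling.** ADA is taken at baseline, Weeks 6, 12 and 24, and in the SFU/EDV column of the protocol's Schedule of Activities (section 1.3). SAP 5.1.1.1.4 maps early-discontinuation (EDV) samples to a scheduled visit.

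**The concern.** Categories 6 and 9 are separate classes, and the incidence sentence removes only the first. Three things follow from the literal wording.

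1. A category 9 participant is in N but can never be in the numerator. Category 9 includes anyone with no post-baseline ADA sample, so an untested person counts as a non-event.
2. The same post-baseline record, one sample missed and the rest negative, leaves N if baseline was positive and stays in N if baseline was negative. The SAP gives no reason.
3. The general rule points the other way. If category 9 counts as missing data, the whole class leaves N.

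Two programmers could therefore build different denominators and each cite the SAP. ADA occurrence on the ECLIA method is a stated objective, and protocol 4.2 says no such data yet exist in adults with RA, so the incidence may be read as a reference figure.

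**Working it through.** The plan states no ADA rate and no expected number in category 9, so there is no planned figure to reproduce. The check has three parts.

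**1. Direct arithmetic**

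Inputs from the documents: 30 enrolled and at least 25 expected to complete Visit 13 (SAP 1.2.2), so up to 30 − 25 = 5 lost by Week 12, or 5/30 = 16.7%.

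Let x be the number of treatment-emergent positives and m the number in category 9. Assume category 6 is empty.

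- Literal reading: x/30.
- All of category 9 removed: x/(30 − m).
- The literal figure equals the other multiplied by (30 − m)/30, which is 0.967 for m = 1, 0.833 for m = 5 and 0.667 for m = 10.

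Example with x = 10 and m = 5, of whom 2 have no post-baseline sample (assumed counts):

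- Literal: 10/30 = 33.3%.
- Only the 2 untested removed: 10/28 = 35.7%.
- All of category 9 removed: 10/25 = 40.0%.

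**2. Why removing all of category 9 is also wrong**

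One positive sample puts a baseline-negative participant in category 2, however many other samples are missing. Category 1 requires negative results at every timepoint. Removing category 9 therefore drops incompletely sampled negatives and keeps incompletely sampled positives, so incidence is biased upward.

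**3. Simulation of the likely size**

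Assumptions: 30 treated, all baseline-negative; four post-baseline samples; true incidence 30%; 5% of samples missing at random; 5 of 30 leaving before Week 12 at uniform times; 10% leaving later; onset split 40/30/20/10% over the four visits; positivity persists once present. What varies is the share of early leavers who give the EDV sample.

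| Leavers giving an EDV sample | Mean untested of 30 | N as written | N with at least one post-baseline sample | Gap |
|---|---|---|---|---|
| None | 2.6 | 25.2% | 27.6% | 2.4 points |
| 80% | 0.5 | 26.6% | 27.1% | 0.5 points |
| 95% | 0.1 | 27.1% | 27.2% | 0.1 points |

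At 80% capture the gap is 0.3 points for a true incidence of 20% and 0.6 points for 40%. With no EDV sample, a companion run gave 16.7% against 18.3% (1.6 points) and 32.9% against 36.2% (3.3 points).

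The spread between the two readings of the current text is larger:

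- No EDV samples: about 25% literal against about 37% with all of category 9 removed, roughly 12 points, with about 9 or 10 of 30 in category 9.
- Full EDV sampling, with onset mostly early: 28.1% against 38.4%, or 10.3 points, with about 8 of 30 in category 9.

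The true value in these runs is 30%, so the second reading overshoots in both cases.

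**The case against.** **Early leavers are scheduled for a sample.** The SFU/EDV column includes ADA, and SAP 5.1.1.1.4 uses ADA sampling as its worked example of mapping an early discontinuation. This stands, and it limits the untested-person effect. Untested participants arise mainly where the EDV is refused or contact is lost.

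**The two sentences can be applied together.** One could take participants with non-missing data and then remove the inconclusive ones. That is possible, so a reader should not infer that the SAP necessarily counts untested people as antibody-free. But the SAP does not say that the rules combine. Its only exception clause is attached to the Safety Set sentence, and the combined reading is the one that overstates incidence. What the text supports is a conflict that needs resolving.

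**Inconclusive may have been meant more widely.** The amendment record in SAP 8.2 shows a definition that takes in missing samples. The current Table 5–2 does not carry it, so it cannot settle how the current sentence is to be read. The difference from the record is not itself an error.

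**The effect is small against sampling error.** The exact 95% interval for 8/30 is 12% to 46%, and one participant in 30 is 3.3 points. This stands for the untested-person effect. It is weaker for a 10-to-12-point gap that depends only on which sentence the programmer follows.

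**Nothing is hidden, and ADA is exploratory.** Categories 1–9 and by-visit status are tabulated and individual results are listed, so a reader could recompute the rate. ADA sits under Other objectives, the named endpoint is status and titer at each assessment, and no hypothesis is tested. All of this stands and keeps the point modest.

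**Conclusion.** The point holds as a denominator rule that is ambiguous and, on its literal reading, treats missing samples inconsistently. Under the assumptions above, the untested-person bias is about 0 to 2.5 points at 30% true incidence and is close to 0 if nearly all leavers give the EDV sample. The spread between the two readings is about 10 to 12 points.

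Three stronger conclusions are not supported:

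- The 10-to-12-point spread is not the bias of the plan as written. It is the distance between two readings, and the higher one is itself biased.
- The opposite handling by baseline status is clear in the text but has no size, because the documents give no rate of baseline positivity and the simulation includes no baseline-positive participants.
- Nothing here affects Cmin or AUC. Membership of the Pharmacokinetic Set does not depend on ADA category.

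A related gap: Table 5–2 has no category for baseline-positive participants with no post-baseline sample. Nor does it cover baseline-negative participants with all samples collected, none positive and some above the drug-tolerance limit. By the literal wording both groups stay in N.

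**What to change.** In SAP 5.5.1.1.2:

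1. Define N as Safety Set participants with at least one post-baseline ADA sample, including a mapped EDV sample, classed as ADA positive or ADA negative under the sample-level status table, whatever their baseline status. A sample classed as inconclusive for drug tolerance does not qualify on its own.
2. Show participants with no such sample in a not-evaluable row outside N.
3. State that this rule overrides the general percentage rule for the incidence table.
4. Print incidence with categories 6 and 9 excluded beside it, labelled as an upper sensitivity figure.

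The cost is a few sentences of SAP text, one table row and one sensitivity line. No new data and no change in conduct are needed. Compared with the literal reading, reported incidence rises slightly or not at all where category 6 is empty. Any category 6 participants with a negative sample would now enter N, which lowers it slightly. Incompletely sampled negatives remain non-events, so some understatement can persist, and the sensitivity figure is there to show how far that could matter.
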